4 OBJECTIVES AND OUTCOME MEASURES

4.1 Primary

Objective	Brief Description/Justification of Outcome Measure	Outcome Measured By	Time Frame

Assess the effectiveness of NRTS compared to ET on 6-month biologically verified 7-day point prevalence abstinence from combusted tobacco
	
Seven day point prevalence abstinence (no combustible tobacco use in the past 7 days) is the recommended outcome for cessation induction trials as it measures a clinically-significant change in the long term, but reflects that participants may quit at any time following the intervention.⁴¹ Biochemical verification with breath carbon monoxide adds additional rigor to the primary outcome.⁴² Carbon monoxide will detect combustible tobacco use and not nicotine replacement therapy use.
	
Self-report survey using timeline follow-back and iCO quit personal CO monitor.
 
Following the CO test and result, we will compute a binary variable: abstinent vs. non-abstinent. Those who report abstinence on all 7 days prior to the 6-month follow-up and have a CO test result of <6ppm will be considered abstinent. Those who report smoking in the past 7 days, or have a CO result >6ppm, or who do not respond to the survey will be classified as non-abstinent.
	
6 months following baseline

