4.2 Secondary

Objective	Brief Description/ Justification of Outcome Measure	Outcome Measured By	Time Frame
Assess the effectiveness of NRTs compared to ET on 1-month self-report 7-day point prevalence abstinence from combusted tobacco	The Society for Nicotine and Tobacco Research recommends measuring outcomes of clinical trials at multiple timepoints to determine at what point interventions may be having an effect. ⁴¹	Self-report survey using timeline follow-back. From the timeline follow-back we will compute a binary variable with those who report no smoking on all 7 days prior to the assessment classified as abstinent, those who report smoking on any of the past 7 days classified as non-abstinent. Those missing smoking status data will be classified as non-abstinent.	1-month following baseline
Assess the effectiveness of NRTs compared to ET on 3-month self-report 7-day point prevalence abstinence from combusted tobacco	The Society for Nicotine and Tobacco Research recommends measuring outcomes of clinical trials at multiple timepoints to determine at what point interventions may be having an effect. ⁴¹	Self-report survey using timeline follow-back. From the timeline follow-back we will compute a binary variable with those who report no smoking on all 7 days prior to the assessment classified as abstinent, those who report smoking on any of the past 7 days classified as non-abstinent. Those missing smoking status data will be classified as non-abstinent.	3-months following baseline

Objective	Brief Description/ Justification of Outcome Measure	Outcome Measured By	Time Frame

Assess the effectiveness of NRTS compared to ET on 24 hour quit attempts.
	
24-hour intentional quit attempts reflect periods of abstinence due to an attempt to quit (not abstinence due to other reasons such as hospitalization etc.). FreSH is a cessation induction study. Thus, we measure the effect of NRTS to induce cessation behavior including quit attempts.
	
Self-report survey item from the Phenx toolkit. We will measure this item on the 1-, 3- and 6-month follow-up survey. We will then create a dichotomous variable indicating whether there has been a quit attempt at any time in the past 6 months by classifying any participant reporting a quit attempt on any follow-up survey as having had a quit attempt. Those who did not report a quit attempt on any survey will be classified as not having a quit attempt.
	
6 months following baseline

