Objective	Brief Description/ Justification of Outcome Measure	Outcome Measured By	Time Frame

Assess the effectiveness of NRTS compared to ET on smoking heaviness
	
In addition to assessing the effectiveness of NRTS on abstinence, we want to assess the effect of NRTS on cessation-related behavior including reducing heaviness of smoking.
	
Smoking heaviness indicates cigarettes per day. Timeline follow-back measure of cigarettes per day on each of the past 7 days at 6-months post quit. We will measure cigarettes per day at baseline. We will then compute cigarettes per day at each follow-up timepoint by summing the number of cigarettes each person reports on each day of their follow-up survey and dividing by 7.
	
6 months following baseline.

Assess whether cessation medication utilization mediates the effectiveness of NRTS on 6-month abstinence.
	
Treatment utilization is one mechanism by which NRTS is hypothesized to have its effect.
	
Self-report survey items of use of the nicotine patch and nicotine lozenge at 1-, 3-, and 6- months post baseline. These items will be dichotomized as used NRT vs. hasn't used NRT in the 6 months post intervention. In addition, days of NRT use will be computed.
	
6-months following baseline.

Objective	Brief Description/ Justification of Outcome Measure	Outcome Measured By	Time Frame

Assess whether attitudes towards NRT (safety and efficacy) mediate the effectiveness of NRTS on 6-month abstinence.
	
We hypothesize that one mechanism of action of NRTS is to cause more favorable attitudes towards NRT.
	
Self-report survey items at baseline, 1-month, 3-month and 6-month surveys of perceptions of nicotine replacement therapy safety and efficacy. We will assess perceptions of NRT efficacy on a 5-point Likert-scale where higher scores indicate greater efficacy. We will assess safety with a single item measure on a 5-point Likert scale where higher scores indicate greater perceptions of NRT safety.
	
6-months following baseline.

Objective	Brief Description/ Justification of Outcome Measure	Outcome Measured By	Time Frame

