9.1.3 After visit survey (Target day 0, in dental practice or remotely)

Following the dental visit, participants will be sent a link via email or text with an after-visit survey. If participants do not respond to the survey within 3 days, they will receive a phone call from Hennepin Healthcare study staff. They will be paid \$20 for after visit survey completion.

The after-visit survey will assess the following:

- the elements of ask-advise-refer as a fidelity check (asked about smoking, advised to quit, asked about interest in quitting, discussed medications, advised to use medication, provided with medication, referred to quit line)
- Demographics (educational attainment, urban/suburban/rural community, zip code, number in household, income, health insurance, dental insurance)
- oral health status
- relationship with dentist
- other non-cigarette tobacco product use
- acceptability of the intervention

9.1.4 1-month follow-up survey (target day 30, conducted remotely)

The one-month follow-up survey will be conducted via email or text. Participants who do not respond will be followed up by phone and/or mail. Participants will be paid \$20 for survey completion.

The one-month follow-up survey will assess the following:

- smoking behavior (smoking each day for the past 7 days, date of last cigarette)
- use of other tobacco products (electronic cigarettes, hookah, cigars, chewing tobacco, snus, pipes, other)
- quit attempts
- use of nicotine patch and lozenge (including sample patches and patches purchased outside of study; use in past 7 days, ever use)
- reasons for nicotine patch/lozenge use
- perceived patch/lozenge effectiveness
- enjoyment of patch/lozenge
- use/purchase of smoking cessation medications,
- use of smoking cessation counseling
- patch/lozenge side effects (nausea, headache, heartburn, mouth soreness, dizziness, dry mouth, sore jaw, excessive salivation, insomnia, hiccups, burning in throat/mouth, skin irritation, skin redness, skin itchiness)

- belief that side effects were caused by patch/lozenge
- perceived oral health status
- frequency of toothbrushing
- type of toothbrush
- interest in stopping smoking
- readiness to quit
- attitudes about nicotine patch, lozenges.

9.1.5 3-month follow-up survey (Target day 90, conducted remotely)

The 3-month follow-up survey will be conducted via email or text. Participants who do not respond will be followed up by phone and/or mail. Participants will be paid \$20 for survey completion.

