The 3-month follow-up survey will assess the following:

- smoking behavior (smoking each day for the past 7 days, date of last cigarette)
- use of other tobacco products (electronic cigarettes, hookah, cigars, chewing tobacco, snus, pipes, other)
- quit attempts
- use of nicotine patch and lozenge (including sample patches and patches purchased outside of study; use in past 7 days, ever use)
- reasons for nicotine patch/lozenge use
- perceived patch/lozenge effectiveness
- enjoyment of patch/lozenge
- use/purchase of smoking cessation medications,
- use of smoking cessation counseling
- patch/lozenge side effects (nausea, headache, heartburn, mouth soreness, dizziness, dry mouth, sore jaw, excessive salivation, insomnia, hiccups, burning in throat/mouth, skin irritation, skin redness, skin itchiness)
- belief that side effects were caused by patch/lozenge
- perceived oral health status
- frequency of toothbrushing
- type of toothbrush
- interest in stopping smoking
- readiness to quit
- attitudes about nicotine patch, lozenges.

9.1.5 6-month follow-up survey (Target day 180, conducted remotely)

The 6-month follow-up survey will be conducted via email or text. Participants who do not respond will be followed up by phone and/or mail. Participants will be paid \$20 for survey completion.

The 6-month follow-up survey will assess the following:

- smoking behavior (smoking each day for the past 7 days, date of last cigarette)
- use of other tobacco products (electronic cigarettes, hookah, cigars, chewing tobacco, snus, pipes, other)
- quit attempts
- use of nicotine patch and lozenge (including sample patches and patches purchased outside of study; use in past 7 days, ever use)
- reasons for nicotine patch/lozenge use
- perceived patch/lozenge effectiveness
- enjoyment of patch/lozenge
- use/purchase of smoking cessation medications,
- use of smoking cessation counseling
- patch/lozenge side effects (nausea, headache, heartburn, mouth soreness, dizziness, dry mouth, sore jaw, excessive salivation, insomnia, hiccups, burning in throat/mouth, skin irritation, skin redness, skin itchiness)
- belief that side effects were caused by patch/lozenge
- perceived oral health status
- frequency of toothbrushing
- type of toothbrush
- interest in stopping smoking
- readiness to quit
- attitudes about nicotine patch, lozenges.

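### Abstinence is defined for all combusted tobacco, but the self-report rule reads only a cigarette timeline follow-back; the cigar, hookah and pipe item enters no rule, which matters most at 1 and 3 months

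*Protocol*

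**What the plan says.** Section 4.1 gives the primary outcome as "Seven day point prevalence abstinence (no combustible tobacco use in the past 7 days". The objectives in 4.2 for 1 and 3 months also name combusted tobacco.

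The classification rules are:

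- **6 months (4.1).** The instruments are "Self-report survey using timeline follow-back and iCO quit personal CO monitor". Patients who report abstinence on all 7 days and "have a CO test result of <6ppm will be considered abstinent". The non-abstinent class is "Those who report smoking in the past 7 days, or have a CO result >6ppm, or who do not respond to the survey".
- **1 and 3 months (4.2).** The variable is computed from the timeline follow-back alone, with "those who report no smoking on all 7 days prior to the assessment classified as abstinent". No CO test is taken.

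The smoking-heaviness row of 4.2 is the only place that spells out what the follow-back records: "Timeline follow-back measure of cigarettes per day on each of the past 7 days". The follow-up surveys in 9.1.4 and 9.1.5 list "smoking behavior (smoking each day for the past 7 days, date of last cigarette" and, as a separate item, "use of other tobacco products (electronic cigarettes, hookah, cigars, chewing tobacco, snus, pipes, other".

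**The concern.** The named endpoint covers every combusted product, while the self-report rule appears to read cigarettes only. Cigars, hookah and pipes are combusted tobacco, yet the item that asks about them has no role in the rule. A patient who stops cigarettes and goes on with, or moves to, one of these products would then meet the self-report definition of abstinence from combusted tobacco.

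Such patients can enrol. Section 6.1 requires near-daily cigarette smoking, and 6.2 does not exclude use of other tobacco. The after-visit survey (9.1.3) asks about non-cigarette tobacco, so the protocol expects some.

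At stake is whether the outcome measures what the objective names. The 1- and 3-month outcomes are reported in their own right, and the cross-lagged mediation model in 12.3 uses earlier values of the outcome. Any error left at 6 months carries into cost per quit, which 12.3 bases on the primary outcome.

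**Working it through.** The main check sets the passages side by side.

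1. **Concept.** All combusted tobacco, 7 days (4.1; objectives in 4.2).
2. **Self-report instrument.** Timeline follow-back at all three times (4.1, 4.2). Its content is described once, as cigarettes on each day (4.2, smoking heaviness). The survey lists pair it with the date of the last cigarette (9.1.4, 9.1.5).
3. **Other combusted products.** Asked separately in all three follow-up surveys, in one bullet that mixes combusted products (hookah, cigars, pipes) with non-combusted ones (e-cigarettes, chewing tobacco, snus). The bullet states no recall window. The patch and lozenge bullet in the same list does.
4. **Rules.** Neither 4.1 nor 4.2 names the separate item.
5. **1 and 3 months.** With zero cigarettes on 7 days and cigars on some of them, the rule in 4.2 returns abstinent. Nothing else in the rule can reverse that.
6. **6 months.** The same patient is sent a CO monitor and must also read below 6 ppm. Under 9.1.6 the monitor is mailed after the survey, with daily reminders for up to 14 days. The windows in 8.3 are days 173-210 for the survey and 174-234 for the test. The test is one reading on a later date, so it cannot verify the 7 days recalled in the survey.

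**Can the size be derived?** No. The documents give no rate of other combusted use among patients who have stopped cigarettes. The sample-size figure itself is sound. With ICC 0.013 and 24 patients per practice (12.2):

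- Design effect = 1 + (24 - 1) x 0.013 = 1.299.
- Effective n per arm = 600 / 1.299 = 461.9.
- Standard error at 5.5% v 10.5% = sqrt[(0.055 x 0.945 + 0.105 x 0.895) / 461.9] = 0.01778.
- Power = Phi(0.05 / 0.01778 - 1.96) = 80.3%, as in Table 11.1.

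Two assumed patterns then give opposite answers on what a stricter rule does to power:

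| Assumed pattern | Power |
|---|---|
| A. The planned 5.5% and 10.5% include false quitters, and the stricter rule removes the same share from each arm: 5%, 10%, 15%, 20% | 80.3% falls to 78.1%, 75.7%, 73.1%, 70.3% under the stricter rule |
| B. True rates are 5.5% and 10.5%, and the present rule adds false quitters equally to both arms: 0.5, 1, 2 points | 78.1%, 76.0%, 72.0% under the present rule; the stricter rule restores 80.3% |

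Under A the stricter rule lowers calculated power; under B it raises it. The documents do not say which applies, or at what level.

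**The case against.** The strongest reply concerns the primary outcome. A reader might infer that it is classified from cigarette reports alone, so that anyone still smoking cigars or a pipe is a quitter at 6 months. The documents do not support that. Section 4.1 also requires CO below 6 ppm and states that CO detects combustible tobacco, which makes it a check that does not depend on the product. This stands, and it narrows the primary-outcome problem to patients whose single later reading is below the cut-off. The documents do not say how often that would happen. The safeguard also needs the test in both arms: 9.1.6 sends the monitor to everyone who reports abstinence, but 6.3 mentions only NRTS patients. The two sections must be reconciled.

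Second, the cigarette-only reading is an inference. The rules in 4.1 and 4.2 speak of smoking and abstinence, and the cigarettes-per-day description belongs to another outcome. This is fair. But it is the only description of the instrument, and the survey pairing points the same way. If *smoking* is meant to cover every combusted product, the protocol does not say so.

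Third, 9.1.4 and 9.1.5 are topic lists, so a recall window missing from a bullet may be present in the questionnaire. This also stands, so the fix asks for the window to be confirmed rather than asserting that it is absent. Leaving the matter to the SAP is a weaker answer. The protocol already fixes the rule in 4.1 and 4.2, and a recall frame that was not asked cannot be recovered at analysis.

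Finally, a reader might infer a definite loss of power. Patterns A and B show why none can be stated.

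**Conclusion.** The concern holds as a mismatch between the endpoint and its self-report rule. It is clearest for the 1- and 3-month secondary outcomes, where the rule as written can class a continuing cigar, hookah or pipe smoker as abstinent from combusted tobacco. For the primary outcome it is a residual gap: the CO criterion mitigates it, but one test after the survey may not close it.

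The conclusion rests on one inference, that the timeline follow-back used for abstinence is the cigarette measure described under smoking heaviness. If it covers all combusted products, a sentence saying so in 4.1 and 4.2 would settle the self-report gap.

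No size can be attached. The power figures in 12.2 are not in error, and the documents support neither a number of false quitters nor a direction of bias between arms.

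**What to change.** In 4.1 and 4.2, class a patient as abstinent only if the timeline follow-back shows no cigarettes on all 7 days **and** the patient reports no hookah, cigar, pipe or other combusted product in the past 7 days. At 6 months keep the CO criterion in addition. State that e-cigarettes, chewing tobacco and snus do not count against abstinence.

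In 9.1.4 and both sections numbered 9.1.5, make sure the other-tobacco item separates combusted from non-combusted products (including under *other*) and has a past-7-days frame.

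The cost is wording in two sections and, if the questionnaire lacks the split or the window, a change to one existing item. No new assessment is needed. Any survey already completed without the window could not support the stricter rule in full. The downside is that reported abstinence rates may be slightly lower.

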4.2 Secondary

Objective	Brief Description/ Justification of Outcome Measure	Outcome Measured By	Time Frame
Assess the effectiveness of NRTs compared to ET on 1-month self-report 7-day point prevalence abstinence from combusted tobacco	The Society for Nicotine and Tobacco Research recommends measuring outcomes of clinical trials at multiple timepoints to determine at what point interventions may be having an effect. ⁴¹	Self-report survey using timeline follow-back. From the timeline follow-back we will compute a binary variable with those who report no smoking on all 7 days prior to the assessment classified as abstinent, those who report smoking on any of the past 7 days classified as non-abstinent. Those missing smoking status data will be classified as non-abstinent.	1-month following baseline
Assess the effectiveness of NRTs compared to ET on 3-month self-report 7-day point prevalence abstinence from combusted tobacco	The Society for Nicotine and Tobacco Research recommends measuring outcomes of clinical trials at multiple timepoints to determine at what point interventions may be having an effect. ⁴¹	Self-report survey using timeline follow-back. From the timeline follow-back we will compute a binary variable with those who report no smoking on all 7 days prior to the assessment classified as abstinent, those who report smoking on any of the past 7 days classified as non-abstinent. Those missing smoking status data will be classified as non-abstinent.	3-months following baseline

Objective	Brief Description/ Justification of Outcome Measure	Outcome Measured By	Time Frame

Assess the effectiveness of NRTS compared to ET on 24 hour quit attempts.
	
24-hour intentional quit attempts reflect periods of abstinence due to an attempt to quit (not abstinence due to other reasons such as hospitalization etc.). FreSH is a cessation induction study. Thus, we measure the effect of NRTS to induce cessation behavior including quit attempts.
	
Self-report survey item from the Phenx toolkit. We will measure this item on the 1-, 3- and 6-month follow-up survey. We will then create a dichotomous variable indicating whether there has been a quit attempt at any time in the past 6 months by classifying any participant reporting a quit attempt on any follow-up survey as having had a quit attempt. Those who did not report a quit attempt on any survey will be classified as not having a quit attempt.
	
6 months following baseline

Objective	Brief Description/ Justification of Outcome Measure	Outcome Measured By	Time Frame

Assess the effectiveness of NRTS compared to ET on smoking heaviness
	
In addition to assessing the effectiveness of NRTS on abstinence, we want to assess the effect of NRTS on cessation-related behavior including reducing heaviness of smoking.
	
Smoking heaviness indicates cigarettes per day. Timeline follow-back measure of cigarettes per day on each of the past 7 days at 6-months post quit. We will measure cigarettes per day at baseline. We will then compute cigarettes per day at each follow-up timepoint by summing the number of cigarettes each person reports on each day of their follow-up survey and dividing by 7.
	
6 months following baseline.

Assess whether cessation medication utilization mediates the effectiveness of NRTS on 6-month abstinence.
	
Treatment utilization is one mechanism by which NRTS is hypothesized to have its effect.
	
Self-report survey items of use of the nicotine patch and nicotine lozenge at 1-, 3-, and 6- months post baseline. These items will be dichotomized as used NRT vs. hasn't used NRT in the 6 months post intervention. In addition, days of NRT use will be computed.
	
6-months following baseline.

Objective	Brief Description/ Justification of Outcome Measure	Outcome Measured By	Time Frame

Assess whether attitudes towards NRT (safety and efficacy) mediate the effectiveness of NRTS on 6-month abstinence.
	
We hypothesize that one mechanism of action of NRTS is to cause more favorable attitudes towards NRT.
	
Self-report survey items at baseline, 1-month, 3-month and 6-month surveys of perceptions of nicotine replacement therapy safety and efficacy. We will assess perceptions of NRT efficacy on a 5-point Likert-scale where higher scores indicate greater efficacy. We will assess safety with a single item measure on a 5-point Likert scale where higher scores indicate greater perceptions of NRT safety.
	
6-months following baseline.

Objective	Brief Description/ Justification of Outcome Measure	Outcome Measured By	Time Frame

Assess whether intention to use NRT mediates the effectiveness of NRTS on 6-month abstinence.
	
We hypothesize that one mechanism of action of NRTS is increase intentions to use NRT.
	
Intention to use NRT is measured at baseline and at 1-, 3-, and 6- month follow-up. Self-report survey item of intention to use nicotine patch and nicotine lozenge in the next 6 months. Intention to use the nicotine patch and nicotine lozenge will be assessed using 2 items regarding intentions to use nicotine patch and nicotine lozenge in one of 5 categories (currently using, plan to use in the next 30 days, plan to use in the next 6 months, may use some day, will never use).
	
6-months following baseline.

Objective	Brief Description/ Justification of Outcome Measure	Outcome Measured By	Time Frame

Assess whether intention to quit smoking mediates the effectiveness of NRTS on 6-month abstinence.
	
We hypothesize that one mechanism of action of NRTS is to increase intention to quit smoking.
	
We will assess intention to quit smoking at baseline, 1-month, 3-months and 6-months using a self-report survey item from the PHENX toolkit on intention to quit smoking in the next 6 months. The item asks if the patient is planning to quit in the next 6 months with 4 answer choices: yes in the next 30 days, yes in the next 6 months, no in the next 6 months, already quit.
	
6-months following baseline.


Assess feasibility and acceptability of the NRTS intervention to practitioners, staff and patients to aid in future implementation through a multi-stakeholder process evaluation.
	
Clinical trials are often conducted without regard to implementation concerns. Collecting implementation data along with effectiveness data can speed the time in which it takes effective interventions to be implemented in real-world practice.
	
Feasibility and acceptability will be measured 3 ways:
 
(1) Surveys: Patients: to assess acceptability, patients will complete the client satisfaction questionnaire regarding the FreSH study interventions given during the after-visit survey.
 
Practitioners and staff will be measured using the Organizational Readiness to Implement Change measure (completed by the main interventionist at the site) prior to and following site data collection. In addition, practitioners and staff involved in the study will complete the Acceptability of Intervention Measure and the Appropriateness of Intervention measure and Feasibility of Intervention measure prior to and following site data collection. Additionally, the amount of time it takes practitioners to administer the intervention will be timed via REDCap.
	
For practitioners and staff, surveys will be given at the beginning and end of site data collection.
 
For patients, surveys will be given approximately one day following their visit.
 
Interviews will be done at the end of study participation for patients and practitioners.
 
Administrative data will be collected for the duration of study recruitment.

---	---	---	--

Objective	Brief Description/ Justification of Outcome Measure	Outcome Measured By	Time Frame
		
(2) Interviews: 10-12 patients, 10-12 dentists and 10-12 other staff in study sites assigned to the NRTS condition will participate in interviews at the end of site data collection regarding the feasibility and acceptability of the NRTS intervention.
 
(3) Administrative data: we will assess feasibility of the intervention by assessing the number of patients qualifying for the intervention (NRTS), the number qualifying who are offered the intervention. We will assess acceptability by the number of patients offered the intervention who accept it.
	

Objective	Brief Description/ Justification of Outcome Measure	Outcome Measured By	Time Frame

Assess the cost effectiveness of the NRTS intervention.
	
To aid in future implementation, we will determine how much the intervention costs relative to how effective the intervention is at increasing abstinence from smoking.
	
We will assess cost per quit and cost per quality adjusted life year. Costs of the intervention will be determined by the value of time for practitioners to take the AAR training, provide AAR to patients, and counsel on NRT use, the costs for the ADA brochures, NRT (based on national average purchase price), and any additional smoking cessation services used by participants (based on national average purchase price). Quality adjusted life years will be estimated based on differences in future healthcare costs based on existing literature.
	
N/A

